## 7.7.1 Replacement of Withdrawn Participants

Participants who are withdrawn by the Investigator due to ineligibility identified during the index surgery will be replaced. Any participants who withdraw their consent to participate prior to their index surgical procedure will also be replaced. Participants who withdraw their consent at any time following their index surgical procedure will not be replaced.

This document contains information that is confidential and proprietary to Smith & Nephew PLC and Smith & Nephew, Inc. and is intended for use only by Smith & Nephew and its manufacturer. It shall not be reproduced or copied in whole or in part, nor shall the contents be disclosed by any means without prior written permission from Smith & Nephew, nor shall anyone make any use of it that is contrary to the expressed or implied wishes of Smith & Nephew.

Study Protocol—Device	smith&nephew
lieu of standard arthroscopic repair of high-grade (>50%)	Number: REGEN.PUB.2018.09
	Version: 3.0, 10SEP2019
partial-thickness tears	Page: Page 24 of 105

## 8. STUDY DESIGN

#### 8.1 STUDY DESIGN

This is a prospective, non-blinded, multi-center cohort study to collect relevant clinical data and compare the REGENETEN Implant in lieu of standard arthroscopic repair in 118 participants (59 participants per group) with a high-grade (>50% tendon thickness) partial-thickness rotator cuff tear.

Up to 12 clinical sites in the United States will enroll and follow 118 participants who meet the study eligibility criteria. Follow-up clinical assessments will be performed at 3 months (±30 days), 6 months (±30 days), 12 months (±30 days), 18 months (±60 days), and 24 months (±60 days) post-operatively.

The total estimated study duration will be 42 months: 18 months enrollment (estimated) and up to 24 months follow-up (primary endpoint assessed at 3 month follow-up) post-operatively.

#### 8.2 ALLOCATION AND BLINDING

This study is not randomized. Selection of the surgical approach (repair with REGENETEN versus standard repair techniques) will be at the discretion of the Investigator, in consultation with the participant, as appropriate.

Standard surgical repair techniques of the rotator cuff will be defined as either:

- 1. Debridement and a transtendinous repair, or
- 2. Complete takedown and repair.

To ensure an equal number of participants enrolled into each treatment group, the Sponsor and Contract Research Organization (CRO) will continuously monitor enrollment and will close enrollment into the faster enrolling cohort (REGENETEN cohort or standard repair technique

This document contains information that is confidential and proprietary to Smith & Nephew PLC and Smith & Nephew, Inc. and is intended for use only by Smith & Nephew and its manufacturer. It shall not be reproduced or copied in whole or in part, nor shall the contents be disclosed by any means without prior written permission from Smith & Nephew, nor shall anyone make any use of it that is contrary to the expressed or implied wishes of Smith & Nephew.

Study Protocol—Device	Smith&nephew
	Number:           REGEN.PUB.2018.09           Version: 3.0, 10SEP2019           Page: Page 25 of 105

cohort) once the targeted enrollment has been reached. Enrollment into the slower enrolling cohort will continue until the study is fully enrolled.

## 8.3 STUDY ENDPOINTS

## 8.3.1 Primary Endpoint

The primary endpoint of this study is the American Shoulder and Elbow Surgeons (ASES) score at 3 months following index surgery.

## 8.3.2 Secondary Endpoints

The secondary endpoints of this study include performance endpoints and economic endpoints. The performance endpoints are:

- 1. ASES score over initial 3 months following index surgery
- 2. Single Assessment Numeric Evaluation (SANE) score over initial 3 months following index surgery
- 3. ASES Visual Analog Scale (VAS) pain score over initial 3 months following index surgery
- 4. ASES score at 6, 12, 18 and 24 months following index surgery
- 5. SANE score at 6, 12, 18 and 24 months following index surgery
- 6. ASES VAS pain score at 6, 12, 18 and 24 months following index surgery
- 7. Constant-Murley score at 3, 6, 12 and 24 months following index surgery
- 8. Cumulative opioid use to treat the index shoulder over 3 months following index surgery
- 9. Cumulative non-opioid prescription medication use to treat the index shoulder over 3 months following index surgery
- 10. Cumulative opioid use to treat the index shoulder over 12 months following index surgery
- 11. Cumulative non-opioid prescription medication use to treat the index shoulder over 12 months following index surgery
- 12. Duration of shoulder immobilization following index surgery
- 13. Time to return to work by work type (sedentary; laborer)
- 14. Time to return to driving

This document contains information that is confidential and proprietary to Smith & Nephew PLC and Smith & Nephew, Inc. and is intended for use only by Smith & Nephew and its manufacturer. It shall not be reproduced or copied in whole or in part, nor shall the contents be disclosed by any means without prior written permission from Smith & Nephew, nor shall anyone make any use of it that is contrary to the expressed or implied wishes of Smith & Nephew.

Study Protocol—Device	Smith&nephew
	Number: REGEN.PUB.2018.09
lieu of standard arthroscopic repair of high-grade (>50%) partial-thickness tears	Version: 3.0, 10SEP2019
	Page: Page 26 of 105

- 15. Time to return to sports
- 16. Incidence of progression to full-thickness tear within 12 months following index surgery
- 17. Incidence of progression to full-thickness tear within 24 months following index surgery
- 18. MRI assessment of percent filling at 12 months following index surgery
- 19. MRI assessment of percent filling at 24 months following index surgery
- 20. Rotator cuff tendon thickness at 12 months following index surgery
- 21. Rotator cuff tendon thickness at 24 months following index surgery
- 22. Goutallier classification of rotator cuff at 12 months following index surgery
- 23. Goutallier classification of rotator cuff at 24 months following index surgery
- 24. Sugaya score of rotator cuff at 12 months following index surgery
- 25. Sugaya score of rotator cuff at 24 months following index surgery
- 26. Incidence of revision surgery within 24 months following index surgery (index shoulder; all causes

The economic endpoints are:

- 27. Aggregate related health care utilization costs over 12 months following index surgery
- 28. Operating room time (index surgery)
- 29. Number of steroid injections over 12 months following index surgery
- 30. Number of unscheduled clinic visits over 12 months following index surgery
- 31. Number of for-cause imaging procedures over 12 months following index surgery
- 32. Number of physiotherapy sessions over 12 months following index surgery

#### 8.4 METHODS USED TO MINIMIZE BIAS AND MAXIMIZE VALIDITY

The study will be conducted at up to 12 clinical sites, reducing the risk of bias inherent in a singlecenter study. To eliminate the potential for selection bias, Investigators will consecutively screen all patients over the age of 18 years who are candidates for arthroscopic surgical treatment of high-grade (>50%) partial-thickness rotator cuff tears.

This document contains information that is confidential and proprietary to Smith & Nephew PLC and Smith & Nephew, Inc. and is intended for use only by Smith & Nephew and its manufacturer. It shall not be reproduced or copied in whole or in part, nor shall the contents be disclosed by any means without prior written permission from Smith & Nephew, nor shall anyone make any use of it that is contrary to the expressed or implied wishes of Smith & Nephew.

Study Protocol—Device	Smith&nephew
lieu of standard arthroscopic repair of high-grade (>50%)	Number: REGEN.PUB.2018.09
	Version: 3.0, 10SEP2019
	Page: Page 27 of 105

## 9. STUDY PROCEDURES

#### 9.1 VISITS AND EXAMINATIONS

## 9.1.1 Summary

For a summary of the required procedures by visit, refer to Table 1: Study Procedures by Visit.

Table 1: Study Proc	cedures by vis	it					
Schedule of Events	Pre-Op (days -60 to -1)	Surgery (day 0)	3 Mo (±30 days)	6 Mo (±30 days)	12 Mo (±30 days)	18 Mo (±60 days)	24 Mo (±60 days)
Informed Consent	$\checkmark$						
Inclusion/Exclusion	✓						
Demographics/ Medical History	✓						
Operative Data		$\checkmark$					
ASES Score	~		√ †	~	~	~	~
SANE	~		√ †	~	$\checkmark$	$\checkmark$	~
Constant-Murley Score	✓		~	~	$\checkmark$		~
Participant Diary			✓‡	√‡	√ ‡		
Adverse Events		$\checkmark$	~	$\checkmark$	$\checkmark$	$\checkmark$	~
Heath Care Utilization			~	~	~		
Revision Surgery			~	~	~	~	~
Upper Extremity MRI	√*				~		~

## Table 1: Study Procedures by Visit

*Pre-Op indicates pre-operative; Mo, month(s); SANE, Single Assessment Numeric Evaluation; ASES, American Shoulder and Elbow Surgeons Score including VAS Pain* 

†The ASES score and SANE will be completed every week (i.e., every 7±3 days) though 3 month follow-up. ‡Participant diaries will be used to document opioid and non-opioid prescription medication use, use of a sling, other related healthcare utilization (i.e. steroid injections, clinic visits, imaging, physiotherapy sessions, etc.) and return to work, driving, and sports. Participant diary will be updated weekly (7±3 days) through 3 month follow-up and monthly (30±7 days) thereafter until 12 months post-surgery.

\*The pre-op MRI is the participant's standard of care MRI and will not follow the study MRI Image Acquisition Protocol which is used for the 12 and 24 month MRIs. The pre-op MRI must occur within 6 months of enrollment into this study. All MRIs will be submitted to the imaging vendor per the Image Transfer Protocol.

## 9.1.2 Pre-operative Visit (60 days to 1 day prior to surgery)

- 1. Screen patient for protocol inclusion and exclusion criteria (based on medical record review and preliminary discussion of study with patient).
- 2. Obtain written informed consent from the participant as detailed in Section 7.4
  - ----- Do not proceed until consent has been obtained -----
- 3. Enter screening data into REDCap Cloud EDC and obtain a Subject ID number.
- 4. Obtain demographic information and medical history, including information on opioid and non-opioid prescription medications used during the past 30 days.
- 5. Complete the ASES questionnaire, SANE questionnaire, and Constant-Murley assessment.
- 6. Obtain copy of the standard of care MRI of index shoulder, if available. Pre-op MRI must have occurred within 6 months of enrollment into this study.
- 7. Confirm date of surgery with participant.

## 9.1.3 Index Surgery (Day 0)

- 1. Confirm eligibility based on arthroscopic visualization of the tear.
- 2. Complete surgical procedure.
- 3. Record operative details as specified in Case Report Forms (CRFs)
- If any adverse events, adverse device effects, or device deficiencies are observed or reported, they must be recorded as instructed in Section 12 – Adverse Events and Device Deficiencies.
- 5. Instruct the participant on proper post-operative care/procedures, including any contraindicated treatments/medication(s).
- 6. Instruct the participant on follow-up procedures, including completing the weekly ASES and SANE questionnaires, completing the weekly diary, and returning for clinical follow-up at 3 months.
- 7. Provide participants with the cohort-specific Physiotherapy Guidelines.

This document contains information that is confidential and proprietary to Smith & Nephew PLC and Smith & Nephew, Inc. and is intended for use only by Smith & Nephew and its manufacturer. It shall not be reproduced or copied in whole or in part, nor shall the contents be disclosed by any means without prior written permission from Smith & Nephew, nor shall anyone make any use of it that is contrary to the expressed or implied wishes of Smith & Nephew.

Study Protocol—Device	Standard Sta
Prospective multi-center study comparing REGENETEN in lieu of standard arthroscopic repair of high-grade (>50%) partial-thickness tears	Number: REGEN.PUB.2018.09
	Version: 3.0, 10SEP2019 Page: Page 29 of 105

## 9.1.4 Weekly Diary (week 1 to week 12 (±3 days))

- 1. Participant will complete the ASES questionnaire and SANE questionnaire.
- 2. Participant will document opioid and non-opioid prescription medication use, use of sling, other healthcare utilization related to the index shoulder (i.e. steroid injections, clinic visits, imaging, physiotherapy sessions, etc.) and return to work, driving, and sports in their diary.
- 3. Study personnel will remind each study participant to complete the questionnaires and diary weekly via telephone, email, or text.
- 4. Study personnel will remind participant of the importance of complying with the specified Physiotherapy Guidelines.

## 9.1.5 3 Month Visit (±30 days), 6 Month Visit (±30 days), 12 Month Visit (±30 days), 18 Month Visit (±60 days), and 24 Month Visit (±60 days)

- 1. Complete the ASES questionnaire (all visits), SANE questionnaire (all visits), and Constant-Murley assessment (3, 6, 12 and 24 month visits only).
- 2. Review diary entries for completeness with participant.
- 3. Document any health care utilization involving the index shoulder not recorded in the participant diary (3, 6, and 12 month visits).
- 4. Document any revision surgeries involving the index shoulder (all visits).
- If any adverse events, adverse device effects, or device deficiencies are observed or reported, they must be recorded as instructed in Section 12 – Adverse Events and Device Deficiencies (all visits).
- 6. MRI of index shoulder (12 month and 24 month visits).
- Instruct the participant on follow-up procedures, including returning for the next clinical follow-up (except for the 24 month exit visit).

This document contains information that is confidential and proprietary to Smith & Nephew PLC and Smith & Nephew, Inc. and is intended for use only by Smith & Nephew and its manufacturer. It shall not be reproduced or copied in whole or in part, nor shall the contents be disclosed by any means without prior written permission from Smith & Nephew, nor shall anyone make any use of it that is contrary to the expressed or implied wishes of Smith & Nephew.

Study Protocol—Device	Smith&nephew
lieu of standard arthroscopic repair of high-grade (>50%)	REGEN.PUB.2018.09
	Version: 3.0, 10SEP2019 Page: Page 30 of 105

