Exclusion Criteria:	
 
Male or female ≥18 years
 
High-grade (>50% tendon thickness) p
 
Failed conservative medical managerras:         
 
a. Four (4) to six (6) weeks of form home exercises
 
b. Activity modification
 
c. Shoulder injection at the discretion
 
 
 
Able to comply with the post-operative schedule
 
Able to speak and read English
 
Provide written informed consent
 
Any one (1) of the following criteria will disparticipation in the study:
 
Prior shoulder surgery on index should enrollment
 
Failed primary rotator cuff surgery of ti
 
Systemic steroid use (oral, IV) or local within 1 month of enrollment
 
Metastatic disease
 
Concomitant surgeries for bone defect (Latarjet procedures) or for superior la posterior (SLAP)
 
Concomitant biceps tenodesis
 
Rheumatoid arthritis
 
Advanced osteoarthritis
 
Fatty infiltration of the index shoulder 10. Chronic pain disorders (i.e., fibromyals 11. History of insulin dependent diabetes 12. History of heavy smoking (> 1 pack per enrollment
 
Currently involved in any injury litigation claims
 
Hypersensitivity to bovine-derived mating 15. Medical or physical condition that, in the would preclude safe participation in the would preclude safe par

	nent of the tendon tear defined al physical therapy or guided of the surgeon physiotherapy and follow-up squalify a patient from der within 12 months of he index shoulder lly injected at the surgical site ts requiring bone implantation abral tear from anterior to rotator cuff muscle ≥ Grade 3 gia) er day) within 6 months of on or workers compensation terials he opinion of the Investigator,		
Study Duration:	18 months enrollment (estimated), 24 mol endpoint assessed at 3 month follow-up)			
Primary endpoint:	ASES (American Shoulder and Elbow Sur following index surgery	rgeons) score at 3 months		

CONFIDENTIAL AND PROPRIETARY This document contains information that is confidential and proprietary to Smith & Nephew PLC and Smith & Nephew, Inc. and is intended for use only by Smith & Nephew and its manufacturer. It shall not be reproduced or copied in whole or in part, nor shall the contents be disclosed by any means without prior written permission from Smith & Nephew, nor shall anyone make any use of it that is contrary to the expressed or implied wishes of Smith & Nephew.

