## 9.2 STUDY ENDPOINTS

## 9.2.1 Performance Endpoints

*American Shoulder and Elbow Surgeons (ASES):* The ASES instrument is composed of 2 sections containing participant self-reported and clinician assessments. The ASES score is a 0 to 100-point rating based solely on participant responses and is a combination of the participant's shoulder pain rating (VAS Pain) and self-reported ability to perform 10 different activities of daily living (ADLs). ASES scores will be recorded pre-operatively, weekly from 1 week to 3 months post-surgery, and at 6,12,18 and 24 months post-surgery.

*Single Assessment Numeric Evaluation (SANE):* The SANE is a simple, single-question, patientbased shoulder function assessment tool: "How would you rate your shoulder today as a percentage of normal (0% to 100% scale with 100% being normal)?" It is popular because of its simplicity and ability to be applied to a wide variety of clinical situations. It has not been validated and no minimal clinically important difference has been reported. SANE scores will be recorded pre-operatively, weekly from 1 week to 3 months post-surgery, and at 6,12,18 and 24 months post-surgery.

Participant-reported Shoulder Pain: Pain in the participant's index shoulder will be assessed using the VAS Pain rating from the ASES instrument. The VAS Pain rating will be recorded pre-

This document contains information that is confidential and proprietary to Smith & Nephew PLC and Smith & Nephew, Inc. and is intended for use only by Smith & Nephew and its manufacturer. It shall not be reproduced or copied in whole or in part, nor shall the contents be disclosed by any means without prior written permission from Smith & Nephew, nor shall anyone make any use of it that is contrary to the expressed or implied wishes of Smith & Nephew.

Study Protocol—Device	% smith&nephew
Urocooctivo militi contor ctilav comparing UE(=ENELEN in	Number:           REGEN.PUB.2018.09           Version: 3.0, 10SEP2019           Page: Page 32 of 105

operatively, weekly from 1 week to 3 months post-surgery, and at 6, 12, 18, and 24 months postsurgery.

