## 10. STATISTICAL DESIGN

A Statistical Analysis Plan (SAP) will be written and finalized prior to database lock. The following is a brief description of the analyses to be described in this plan. If there are any changes from the analysis described below it will be detailed in the SAP and the Clinical Study Report (CSR). Any changes/additions to the analysis described in the SAP will also be detailed in the CSR.

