#### **10.6** INTERIM ANALYSES

A data extract will be completed when the last enrolled participant has completed their threemonth follow-up visit. A report will not accompany this data extract but the findings may be presented as possible podium or conference activity.

This document contains information that is confidential and proprietary to Smith & Nephew PLC and Smith & Nephew, Inc. and is intended for use only by Smith & Nephew and its manufacturer. It shall not be reproduced or copied in whole or in part, nor shall the contents be disclosed by any means without prior written permission from Smith & Nephew, nor shall anyone make any use of it that is contrary to the expressed or implied wishes of Smith & Nephew.

Study Protocol—Device	Smith&nephew
Prospective multi-center study comparing REGENETEN in lieu of standard arthroscopic repair of high-grade (>50%) partial-thickness tears	Number: REGEN.PUB.2018.09
	Version: 3.0, 10SEP2019 Page: Page 47 of 105

An interim analysis will be conducted when the last enrolled participant has completed their oneyear follow-up from index surgery. This analysis will include a simplified statistical report and a possible peer-reviewed publication. Further details will be provided in the SAP.

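### Secondary objectives #1–#3 analyse about 12 weekly scores per participant with a regression that states no week term, no within-participant correlation and no 3-month summary

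*Combined protocol and SAP*

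**What the plan says.** **Weekly scores.** The footnote to Table 1 states: "The ASES score and SANE will be completed every week (i.e., every 7±3 days) though 3 month follow-up". Section 9.1.4 is headed "Weekly Diary (week 1 to week 12 (±3 days" (closing brackets omitted). Section 9.2.1 adds: "ASES scores will be recorded pre-operatively, weekly from 1 week to 3 months post-surgery, and at 6,12,18 and 24 months post-surgery". VAS pain is a component of the ASES, so it follows the same schedule.

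**Objectives #1–#3.** Sections 5.2 and 8.3.2 define these objectives and their endpoints over the first 3 months. Table 2 (Section 10.4.2) takes the weekly scores as outcomes and, in the statistical-test column, gives generalized linear regression adjusted for the baseline score and baseline differences. The means are then compared with an MCID: 11.1 points (ASES), 29.4 points (SANE) and 1.37 cm (VAS). Section 10.1 makes secondary results exploratory unless stated otherwise, promises 95% confidence intervals, and says selected outcomes will be tested as set out in Section 10.4.2.

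**Primary endpoint.** Section 10.4.1 compares mean ASES at 3 months by multiple linear regression adjusted for baseline. Section 8.1 describes "up to 24 months follow-up (primary endpoint assessed at 3 month follow-up) post-operatively" and the Synopsis has "endpoint assessed at 3 month follow-up". Section 9.1.3 item 6 lists the weekly questionnaires separately from the 3-month clinic return. Section 9.1.5 gives the visit windows: "3 Month Visit (±30 days), 6 Month Visit (±30 days), 12 Month Visit (±30 days" (closing bracket omitted).

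**Timing of decisions.** Section 10: "A Statistical Analysis Plan (SAP) will be written and finalized prior to database lock". Section 10.6: "A data extract will be completed when the last enrolled participant has completed their threemonth follow-up visit", and it allows those findings to be presented.

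**The concern.** Each participant contributes up to 12 scores on the same shoulder, and these are correlated. The model named in Table 2 does not say whether the rows are fitted together or week by week, whether week enters the model, or what quantity represents the 3-month period. The text refers to mean scores without saying what they are averaged over.

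At stake is the interval, and with it the clinical-importance statement. Section 10.4.1 classifies a difference by whether its confidence interval lies above, contains or lies below the MCID, and Table 2 carries the MCID comparison into these objectives. An interval that is too narrow makes that classification look more certain than it is. Twelve separate intervals give no single answer to the question the objective asks.

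The second, smaller matter is the primary record. Week 12 (day 84 ± 3) falls inside the 3-month visit window (about day 60 to 120), so most participants should have two ASES scores near 3 months. No sentence says which is analysed.

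**Working it through.** **Inputs from the protocol (Section 11):** difference 11.1; effect size 0.56; 80% power; alpha 0.05 (two-sided, Section 10.4.1); 51 per arm evaluable; 15% dropout; 59 per arm enrolled. Twelve weekly scores come from Section 9.1.4. **Assumptions not in the documents:** exchangeable within-participant correlation ρ of 0.4, 0.6 or 0.8; the same SD every week; a recovery slope of 5 to 10 points per month.

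1. *The plan's own figure.* A two-sided two-sample t-test at d = 0.56 needs 51.03 per arm, which matches the stated 51. Then 51 × 1.15 = 58.65, rounded to 59. This is a single-time-point calculation and uses no weekly data.

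2. *SE at one week.* SD = 11.1/0.56 = 19.82. After dropout, 59 × 0.85 ≈ 50 per cohort. SE = 19.82 × √(2/50) = 3.96.

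3. *Twelve rows pooled as independent.* The reported SE is 3.96/√12 = 1.14. The true SE is larger by √(1 + 11ρ), and coverage is 2Φ(1.96/factor) − 1.

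| ρ | 1 + 11ρ | factor | coverage of a nominal 95% CI | valid SE of the 12-week average, 3.96 × √((1 + 11ρ)/12) |
|---|---|---|---|---|
| 0.4 | 5.4 | 2.32 | 60% | 2.66 |
| 0.6 | 7.6 | 2.76 | 52% | 3.15 |
| 0.8 | 9.8 | 3.13 | 47% | 3.58 |

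4. *Effect of omitting week.* An unmodelled trend inflates the residual variance and so widens the naive interval. At 10 points per month (2.33 per week), weeks 1–12 have variance (144 − 1)/12 = 11.9, which adds 2.33² × 11.9 ≈ 65 to 19.82² = 393. The naive SE rises by √(458/393) = 1.08. At ρ = 0.6 coverage becomes 2Φ(1.96 × 1.08/2.76) − 1 ≈ 56%. This is better than 52% but still far below 95%.

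5. *What this does to the MCID label (ρ = 0.6, no trend).* The naive half-width is 1.96 × 1.14 = 2.2, so the interval contains 11.1 for estimates from 8.9 to 13.3. The valid half-width is 1.96 × 3.15 = 6.2, so the range is 4.9 to 17.3. An estimate of 8 points would be labelled clinically unimportant under the first and possibly important under the second.

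6. *Week-by-week fits.* Each interval has SE 3.96 and is valid, but there are 12 of them and no defined 3-month contrast.

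7. *Primary record.* Sections 8.1, 9.1.3, 9.1.5 and 10.6 all point to the clinic visit. If visit days are balanced between cohorts the bias is zero. Spread that is uniform over ±30 days adds an SD of (slope/30) × 60/√12, which is 2.9 points at 5 per month and 5.8 at 10 per month. Power at 50 per cohort then falls from 79.2% to 78.3% and 75.9% respectively.

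**The case against.** **Detail belongs in the SAP.** Section 10 calls itself a brief description and defers to a SAP whose text is not in the supplied document. Week terms and covariance structure are ordinary SAP content, so their absence from a protocol summary does not prove they are absent from the final plan. This stands as a limit on the finding. It does not settle the timing, because the SAP is due only before database lock while 3-month findings may be presented from the earlier extract.

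**These objectives are exploratory.** No alpha control is promised, so the chance that some week is nominally significant under no effect (about 36%, 28% or 19% at the three correlations) breaks no stated guarantee. That is right, and the finding does not rest on it. But the promised confidence intervals still need to be valid, and they feed the MCID comparison.

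**Pooling as independent rows is a hypothetical.** True: the plan does not say it will do this, and a by-week reading is equally natural. That reading avoids the coverage problem but leaves the 3-month endpoint without an estimate.

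**The primary analysis.** A reader might infer that the primary record is open to choice and that the ±30-day window biases the result. For example, a 10-day gap in mean visit day at 5 to 10 points per month would shift the contrast by 5 × 10/30 = 1.7 to 10 × 10/30 = 3.3 points. The documents do not support that inference. They point to the clinic visit, and nothing in them indicates a cohort gap in visit day. Nor is it an error that the primary model leaves weekly scores unused: a baseline-adjusted regression at one time point is legitimate and matches the sample-size calculation.

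**Conclusion.** The point holds for objectives #1–#3. As written, the model either gives intervals that are too narrow (coverage about 60%, 52% or 47% at assumed correlations 0.4, 0.6 or 0.8, somewhat higher with a week trend) or gives 12 valid intervals with no single estimate of early benefit. The size depends on the assumed correlation and on how the model is actually fitted. The gap itself does not depend on those assumptions. It is a worthwhile, inexpensive improvement to exploratory objectives.

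For the primary endpoint, only a confirming sentence and sensitivity analyses are warranted. Two stronger inferences go beyond the documents. One is that visit timing biases the primary contrast; with balanced timing there is no bias and a power loss of roughly 1 to 3 percentage points under the slopes assumed here. The other is that dropout biases it; a material bias would need, for instance, outcome-related dropout confined to one cohort, which nothing in the documents suggests.

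**What to change.** **Objectives #1–#3.** Specify a repeated-measures model for weekly ASES, SANE and VAS pain with baseline score, prespecified covariates, cohort, week, cohort-by-week and participant-level correlation. Take the weeks 1–12 average contrast as the estimate for each objective and apply the MCID comparison to its interval. An unstructured covariance over 12 weeks needs 12 × 13/2 = 78 parameters from at most 118 participants, so prespecify a structured fallback (for example Toeplitz) with robust standard errors.

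**Support for the primary endpoint.** Report the week-12 ASES contrast from the same model as a supporting analysis, so that participants without a 3-month value contribute their weekly scores. State that this relies on dropout being explained by observed scores.

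**Primary record.** Before the 3-month extract, confirm in one sentence that the clinic-visit ASES is the primary record. Add two sensitivity analyses: one using the week-12 score (±3 days) and one adjusting for actual day since surgery.

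**Cost.** Protocol and SAP wording, modest programming, and reliance on a covariance model. No new data are needed; N = 118 and the primary regression stay as they are.
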